5.2.5.1 Antithrombin Use

Routine use of unfractionated heparin post-procedure is not recommended.

5.2.5.2 Sheath Removal

If femoral access is used, the sheath should be removed when the ACT is ≤ 180 seconds (or aPTT ≤ 50 seconds if ACT unavailable). If radial access is used, the sheath should be removed based on the discretion of the treating physician.

If a closure device is utilized, it will not be necessary to wait until the ACT or aPTT reaches the prescribed levels. Institutional guidelines for ambulating following sheath removal should be followed. Patients may be ambulated while study drug infusions continue if institutional guidelines permit it.

5.2.5.3 Blood Sampling

Whenever institutional policies allow, blood sampling can be obtained from sheaths, catheters, or central lines (including arterial lines) if available. Otherwise, an additional peripheral in-dwelling catheter may be inserted for venous blood sampling (eg, heparin lock).

The following evaluations will be performed at the times indicated (see Schedule of Evaluations and Procedures, Appendix 1; all evaluations and laboratory measurements should be performed within the time specified, unless otherwise specified):

- a. Hemoglobin, hematocrit and platelet count will be sampled at the same time as the troponin draws (see below), i.e., immediately prior to PCI, preferably from the PCI access sheath or guiding catheter, at 9 ± 3 hours following PCI, and at 21 ± 3 hours. If the patient remains in the hospital longer than 36 hours after PCI, a third hemoglobin, hematocrit and platelet count post-PCI draw will be sampled at 42 ± 6 hours after PCI. All hemoglobin, hematocrit and platelet count samples will be analyzed by the local laboratory.
- b. If a platelet count falls below 100,000 cells/ μL and decreases at least 25% from the baseline value in any sample compared to any previous sample, additional repeat platelet counts and/or further laboratory analyses (i.e., microscopic) per local institution guidelines must be performed to exclude laboratory error (clumping, etc.). The repeat platelet counts should be performed according to the specific practice at each institution. See Appendix 7 for guidelines for management of thrombocytopenia.
- c. Troponin (troponin I or troponin T) will be sampled immediately prior to PCI, preferably from the PCI access sheath or guiding catheter, at 9 ± 3 hours following PCI, and at 21 ± 3 hours. If the patient remains in the hospital longer than 36 hours after PCI, a third post-PCI troponin will be sampled at 42 ± 6 hours after PCI. All troponin samples will be analyzed by the local laboratory. It is **mandated** that patients be observed for a minimum of 18 hours following PCI to allow for at least two post-PCI troponin samples.

See Appendix 2 for a complete listing of local laboratory evaluations.

5.2.6 Safety Evaluation, Discharge and Follow-Up

Patients will be assessed for serious adverse events (including serious bleeding events) and non-serious adverse events of interest that occur from the time of study drug initiation

through 48 hours following PCI or hospital discharge, whichever comes first. These events will be documented on the CRF. Some serious adverse events will require expedited reporting (see Adverse Events Section 8.0).

Patients are **mandated** to stay a minimum of 18 hours following PCI to allow for at least two post-PCI troponin samples to be obtained at time-points 9±3 hours and 21±3 hours following PCI. If the patient remains in the hospital longer than 36 hours after PCI, a third post-PCI troponin will be sampled at 42±6 hours after PCI.

5.2.7 Evaluation of Endpoints

Evaluation of death, PPM uTVR and REPLACE-2 Major bleeding and other endpoints will not be adjudicated.

5.2.8 Criteria for Discontinuation of Study Drug

If at any time during the study the Investigator responsible for the clinical care of the patient decides that continued use of the study drug is contraindicated, administration of the study drug should be stopped. Study drug should be discontinued if any of the following develop:

- a. Unusual or excessive bleeding;
Signs or symptoms of abnormal, pathological bleeding from any source that cannot be controlled without discontinuation of the study drug. Hematoma at the site of the vascular sheath insertion is expected and should not serve as a reason to discontinue study drug, unless the bleeding cannot be controlled with normal measures.
- b. Development of a new, neurologic deficit or significant alteration in mental status.
- c. Development of a platelet count <50,000/mm³.
- d. Any serious adverse event possibly related to or exacerbated by study drug administration.
- e. Need for urgent CABG. Appropriate measures should be taken to minimize surgical risk (see Appendix 5 Guidelines for Management of Urgent Target Vessel Revascularization).
- f. Any need for a surgical procedure with the exception of those procedures performed under local anesthesia.

If the study drug is discontinued prematurely, the Sponsor will be notified as soon as possible. A patient for whom study drug is discontinued will continue to be monitored according to the protocol tests and procedures after study drug has been discontinued.

5.2.9 Concomitant Medication(s)/Treatment(s)

Only FDA-approved drugs may be administered in this study. Concomitant oral P2Y₁₂ antagonist medications must be pre-specified prior to randomization.

5.2.9.1 Permitted

Antiplatelet/Anticoagulant agents

The following concomitant antiplatelet/anticoagulant agents are permitted in the study:

- aspirin
- clopidogrel
- prasugrel

- ticagrelor
- unfractionated heparin

The name, timing and dosing of the above antiplatelet/anticoagulant agents should all be recorded on the CRF.

Clopidogrel is contraindicated with prasugrel and ticagrelor; prasugrel is contraindicated with clopidogrel and ticagrelor; and ticagrelor is contraindicated with clopidogrel and prasugrel.

Oral, sublingual, topical, or I.V. nitrates

Any of these medications may be given if necessary based on the discretion of the treating physician. These medications received during the procedure and for 48 hours following PCI or until hospital discharge, whichever comes first will be recorded on CRFs, according to drug class (recording of name, dosage and timing is not required).

Ace-inhibitors, calcium channel blockers, beta-blockers, lipid-lowering therapy, angiotensin receptor blockers, diuretics, digoxin and diabetes medications.

Any of these medications may be given if necessary based on the discretion of the treating physician. These medications received during the procedure and for 48 hours following PCI or until hospital discharge, whichever comes first will be recorded on CRFs, according to drug class (recording of name, dosage and timing is not required).

Nonsteroidal anti-inflammatory agents

Any of these medications may be given if necessary based on the discretion of the treating physician. These medications received during the procedure and for 48 hours following PCI or until hospital discharge, whichever comes first will be recorded on CRFs, according to drug class (recording of name, dosage and timing is not required).

5.2.9.2 Prohibited

Oral anticoagulation

Oral anticoagulation medications (warfarin derivatives) should not be administered until at least 12 hours after completion of the study drug infusions unless INR \leq 1.3.

Antiplatelet/Anticoagulant agents

No other antiplatelet agents (except aspirin, clopidogrel, prasugrel or ticagrelor) or anticoagulant agents (except unfractionated heparin) should be administered until completion of the study drug infusion. Low-molecular-weight heparin should not be administered during infusion of study drug. Dextran may not be used during or prior to study drug infusion.

Thrombolytic agents

Thrombolytic agents must be discontinued for at least 24 hours prior to randomization and may not be used until at least 12 hours after completion of the study drug infusion.

Bivalirudin

Bivalirudin must be discontinued for at least 12 hours prior to randomization and may not be used until at least 12 hours after completion of the study drug infusion.

Ticlopidine

Ticlopidine should not be administered in this study.

Unapproved agents

Therapeutic agents not approved by the FDA at the time of the protocol finalization should be discontinued at least 48 hours prior to randomization and may not be used until after 24 hours following PCI.

5.2.10 Patient Withdrawal

Patients may withdraw at any time during the study without prejudice, or be discontinued from the study at the discretion of the Investigator if medically necessary or if any untoward effects occur. In addition, a patient may be withdrawn by the Investigator or the Sponsor if the patient violates the study plan or for administrative and or other safety reasons. The Investigator or study coordinator must notify the Sponsor immediately (via telephone or fax) when a patient has been discontinued or withdrawn because of an adverse experience. When a patient discontinues or withdraws prior to study completion, all applicable activities scheduled for the end of study should be performed at the time of discontinuation. Any adverse experiences that are present at the time of discontinuation/withdrawal should be reported and followed-up in accordance with the safety requirements outlined in the Adverse Events Section 8.0.

Unless the patient has explicitly withdrawn consent for further data collection, it is important that complete data are obtained for all patients whether or not they receive their assigned treatment or have discontinued study drug. Every attempt should be made to collect information. All procedures and laboratory specimens or tests requested for evaluation following administration of the study drug should be carried out when possible whether or not a patient continues to receive treatment according to the protocol. Discontinued patients will not be replaced.

6.0 PRIMARY EFFICACY MEASUREMENTS

The primary endpoint will be the composite of death, PPM, uTVR or major bleeding (where major bleeding is defined in Section 7.1 and discussed further in Section 9) within 48 hours following PCI or hospital discharge, whichever comes first.

All clinical events from the time of study drug administration will be recorded. The number, type and length of coronary stents placed as well as the outcome of the procedure will be recorded on the CRF.

After study drug administration, the development of any of the following events will be recorded on the appropriate CRF.

6.1 Death

Death due to any cause will be assessed through to 48 hours following PCI or hospital discharge, whichever comes first.

Death will not be adjudicated.

6.2 Periprocedural Myonecrosis

The definition of periprocedural myonecrosis is the following:

Periprocedural myonecrosis will have occurred if there is at least one troponin (troponin I or troponin T) value of ≥ 3 times the upper limit of normal AND at least 20% or greater than the baseline troponin value, per the troponin Local Laboratory, within 48 hours following PCI or hospital discharge, whichever comes first.

Periprocedural myonecrosis will not be adjudicated.

To be included in the primary composite endpoint analysis and in the secondary PPM endpoint analysis, a patient MUST have the pre-PCI troponin Local Laboratory measurement AND at least one troponin Local Laboratory measurement within 48 hours following PCI or hospital discharge, whichever comes first.

Patients without a pre-PCI troponin Local Laboratory measurement will NOT be included in the PPM endpoint analysis, but will still be included in the intention to treat analysis and be analyzed for death and uTVR.

Patients without any troponin Local Laboratory measurements within 48 hours following PCI or hospital discharge, whichever comes first will NOT be included in the PPM endpoint analysis, but will still be included in the intention to treat analysis and be analyzed for death, uTVR and major bleeding.

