9.4 Analysis Population

All efficacy analyses will be performed on the modified intent-to-treat population (MITT) (i.e. randomized patients who underwent PCI and received study drug) and on the per-protocol population (i.e. patients who completed the full course of the study without major protocol violations). Safety analyses will be performed on the safety population (i.e. patients who received any study treatment).

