9.6 Planned Methods of Analysis

General Principles

For continuous variables, descriptive statistics (mean, SD, median, and quartiles) will be tabulated by treatment group. For categorical variables, the number and proportion of patients in each category will be tabulated.

The primary and secondary endpoints will be analyzed using the MITT population. Safety endpoints will be analyzed using the safety population. Demographics, baseline characteristics, and other study assessments will be analyzed using the MITT and intent-to-treat (ITT) population.

Confidence intervals will be used to assess hypotheses of non-inferiority and superiority. Details of the statistical methods will be developed in the Statistical Analysis Plan (SAP).

Demography and Baseline Characteristics

All appropriate background data will be summarized for each treatment group. If there are heterogeneities between two groups in any of the patient characteristics that are of clinical importance or could affect the study outcome, the impact of the imbalances will be investigated. If necessary, adjustments may be made in the efficacy and safety analysis and will be documented in the study report.

Primary Endpoint

The first primary and co-primary endpoints will be analyzed by the use of a one-sided 97.5% confidence interval

Subgroup/Covariate Analyses

Formal subgroup analyses will be performed by including the appropriate interaction terms in multivariable logistic regression models. The effects of potential covariates (see Section 9.3.4) will be assessed using multi-variable logistic regression.

Secondary Endpoints

The analysis of the secondary endpoints will be conducted in the same way as for the primary endpoint.

Safety Endpoints

The analysis of these safety endpoints will compare the incidence in the short tirofiban treatment group to the incidence in the eptifibatide group, the incidence in the short tirofiban treatment group to the incidence in the long tirofiban treatment group and the incidence in the long tirofiban treatment group to the incidence in the eptifibatide group, using the Fisher's mid-p (Berry and Armitage, 1995). Serious adverse events will also be tabulated overall and by severity for each treatment group.

Multiplicity (Multiple Endpoints)

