2.9.1.3 Definition of Composite Endpoint

- Death due to any cause will be assessed through to 48 hours following PCI or hospital discharge, whichever comes first.
- Periprocedural myonecrosis will have occurred if there is at least one troponin (troponin I or troponin T) value of ≥ 3 times the upper limit of normal and at least 20% or greater than the baseline troponin value, per the troponin Local Laboratory, within 48 hours following PCI or hospital discharge, whichever comes first.
 - To be included in the primary composite endpoint analysis and in the secondary PPM endpoint analysis, a patient must have the pre-PCI troponin Local Laboratory measurement and at least one troponin Local Laboratory measurement within 48 hours following PCI or hospital discharge, whichever comes first.

- Patients without a pre-PCI troponin Local Laboratory measurement will not be included in the PPM endpoint analysis but will still be included in the intention to treat analysis and be analyzed for death and uTVR.
 - Patients without any troponin Local Laboratory measurements within 48 hours following PCI or hospital discharge, whichever comes first will not be included in the PPM endpoint analysis but will still be included in the intention to treat analysis and be analyzed for death, uTVR and major bleeding.
- Urgent Target Vessel Revascularization (uTVR) is either a PCI following the index PCI, or any CABG procedure performed after the index PCI on a non-selective basis in the target vessel because of recurrent myocardial ischemia. A revascularization procedure in the target vessel is considered urgent if it is due to one or more episodes of chest pain, presumed to be ischemic in origin and lasting at least 5 minutes, and results in either urgent repeat PCI or urgent coronary artery bypass surgery involving the target vessel. In the absence of pain, new ischemic ST-segment or T-wave changes, acute pulmonary edema, ventricular arrhythmias presumed to be ischemic in origin will constitute sufficient evidence of ischemia. The episode of ischemia leading to urgent repeat PCI must occur following completion of the index PCI and guidewire removal. For uTVR to count towards the primary composite endpoint, uTVR will have to be initiated during the course of the study (i.e., 48 hours following PCI or hospital discharge, whichever comes first).
- Major bleeding is defined using the criteria from the REPLACE-2 trial. Major bleeding is defined as follows:

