3.2 Analysis Population

The Modified Intent-to-treat (mITT) Population is defined as all randomized patients who underwent PCI and received study drug.

The Per Protocol (PP) Population will consist of all randomized patients who completed the full course of the study without major protocol violations.

The Safety Population is defined as all randomized subjects who received any study treatment. All efficacy analyses will be performed on the modified intent-to-treat population (mITT) and on the per-protocol population (PP). Safety analyses will be performed on the safety population.

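### The troponin-entry rule removes patients with a known death, uTVR or major bleed from the primary composite analysis

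*Protocol*

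**What the plan says.** **Entry rule.** Protocol 6.2 says: "To be included in the primary composite endpoint analysis and in the secondary PPM endpoint analysis, a patient MUST have the pre-PCI troponin" measurement, plus at least one post-PCI value in the window. SAP 2.9.1.3 agrees: "a patient must have the pre-PCI troponin Local Laboratory measurement and at least one troponin Local Laboratory measurement within 48 hours following PCI" or discharge. Neither text provides for a patient whose event is already established by another component.

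**The sentences that follow it, in both documents.** "Patients without a pre-PCI troponin Local Laboratory measurement will NOT be included in the PPM endpoint analysis"; such patients "will still be included in the intention to treat analysis and be analyzed for death and uTVR". Patients without any post-PCI troponin are handled the same way, except that major bleeding is added to their list.

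**Population.** Protocol 9.6: "The primary and secondary endpoints will be analyzed using the MITT population". SAP 3.2: "The Modified Intent-to-treat (mITT) Population is defined as all randomized patients who underwent PCI and received study drug". SAP 3.2 otherwise defines only the per-protocol and safety populations. The protocol assigns ITT to other purposes: "Demographics, baseline characteristics, and other study assessments will be analyzed using the MITT and intent-to-treat (ITT) population" (9.6).

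**Primary analysis.** SAP 3.10.1 takes the proportion of patients with at least one of death, periprocedural myonecrosis (PPM), uTVR or REPLACE-2 major bleeding. It claims non-inferiority if the lower bound of C − T exceeds −0.191. SAP 3.13 rules out imputation and adds nothing on a composite in which only PPM is missing.

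**The concern.** A patient who has died, had uTVR or had a major bleed is a composite event whatever the troponin shows. The entry rule nevertheless removes that patient from the primary test if the baseline value or all post-PCI values are missing.

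The exclusion acts after randomization in an open-label trial and can depend on the outcome. The clearest route is death. The first scheduled post-PCI draw is at 9 ± 3 hours (Protocol 5.1), so a patient who dies within 6 hours has no scheduled post-PCI value and would leave a composite that includes death. A patient with a known uTVR or bleed is lost only if samples are missing for some other reason.

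An event lost from the test arm moves the result towards non-inferiority; one lost from the control arm moves it away. Long tirofiban is the control in one co-primary comparison and the test arm in the other.

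The surrounding text does not repair this. It sends the affected patients to an intention-to-treat analysis that is not defined for efficacy, and it leaves major bleeding off the list for the missing-baseline group without a reason.

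**Working it through.** **1. Reproduce the plan's figure.** Inputs (Protocol synopsis, 9.2 and 9.5): 51% in both arms, margin 19.1 points, one-sided alpha 0.025, power 99%.

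n per arm = (1.960 + 2.326)² × 2 × 0.51 × 0.49 / 0.191² = 252, so 504 in total against approximately 500 stated. Power at 250 per arm = Φ(0.191/√(2 × 0.51 × 0.49/250) − 1.96) = 98.96%. The sample size is not in question.

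**2. Effect of k dropped events on an arm of n at 51%.** The fall in the observed rate is 0.51 − (0.51n − k)/(n − k) = 0.49k/(n − k). At n = 250: 0.49/249 = 0.20 points for one event and 2.45/245 = 1.00 point for five.

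**3. Size of the long tirofiban arm.** The stated totals (about 550 overall; 500, 350 and 350 by comparison) do not agree:
- 550 − 500 gives 50.
- Solving 500/350/350 gives 250, 250 and 100, which sum to 600.
- 550 with the two 350s gives 550 − 350 = 200 for each of the other arms, and 150.

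The range is therefore 50 to 150. One dropped event is worth 0.49/49 = 1.00, 0.49/99 = 0.49 or 0.49/149 = 0.33 points at 50, 100 or 150.

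**4. Effect on the bound.** Lower bound = (C − T) − 1.96 × √[T(1 − T)/n_T + C(1 − C)/n_C], with C = 0.51 and events dropped from the test arm only. Results are in percentage points.

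| Test v control | none dropped | one dropped | five dropped |
|---|---|---|---|
| 250 v 250 | −8.76 | −8.58 | −7.81 |
| long 150 v 200 | −10.58 | −10.28 | – |
| long 100 v 250 | −11.59 | −11.14 | – |
| long 50 v 250 | −15.18 | −14.31 | – |

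All are clear of −19.1.

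**5. How the competing texts would score the same data.** Assumed example: eptifibatide 128/250 with complete troponin; 250 on short tirofiban, 12 without troponin, 3 of those with a known event.
- Entry rule as written: 121/238 = 50.8%, bound −8.5.
- Known events added to numerator and denominator: 124/241 = 51.5%, bound −9.1.
- Full mITT, missing troponin counted as no PPM: 124/250 = 49.6%, bound −7.2.

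**6. Can it change the conclusion?** Only near the margin. With eptifibatide 128/250 and 5 short-tirofiban patients without troponin, all with known events, 150/245 gives −18.7 (non-inferior). Counting the five gives 155/250 and −19.4 (not non-inferior).

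**7. Power.** If an assumed 2%, 5% or 10% of each arm were excluded, power for the first test would be 98.84%, 98.62% or 98.18%.

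**The case against.** The entry sentence is explicit and stands in both documents. Death, uTVR and PPM are also secondary endpoints in their own right, so the sentences after it can be read as covering component analyses only. With imputation ruled out, the ordinary result is a complete-case composite within mITT. A reader might infer from the conflicting passages that the primary numerator and denominator are left undefined. That goes too far: the mandatory wording gives a definite rule, and only its link to mITT is unstated. But that rule is the one that drops known events, so the defence settles the ambiguity without answering the main point.

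A reader might also infer that the dropped events disappear, in particular bleeds in patients without a baseline troponin. The SAP does not support that. Mock Table 14 tabulates every component on mITT, Tables 16 and 17 cover death and uTVR separately on mITT, and Tables 20 and 21 cover REPLACE-2 major bleeding on the safety population, which has no troponin condition. The events would be visible, but not counted in the primary test.

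Finally, loss should be rare. Sampling is mandated, and Protocol 5.2.8 and 5.2.10 continue tests after study drug stops. This stands, and it limits the size of the problem.

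**Conclusion.** The point holds as a defect in the primary endpoint rule. As written, it excludes known composite events and contradicts both the at-least-one-component count in SAP 3.10.1 and the mITT definition. It should be fixed, because the correction is cheap and the primary test should not depend on which passage is programmed.

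The effect is probably small. At the planning assumptions one dropped test-arm event moves the bound by 0.18 points in the first comparison (8.76 − 8.58), and by 0.30 to 0.87 points when long tirofiban is the test arm. Power hardly changes. These figures rest on a 51% rate in both arms, assumed numbers of dropped events and arm sizes inferred from inconsistent totals; the documents give no missing-troponin rate.

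A reader might infer that the rule biases the trial towards tirofiban. The documents do not show that: the direction depends on which arm loses events, and nothing indicates a difference between arms.

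**What to change.** In Protocol 6.2 and SAP 2.9.1.3:
1. Count any patient in the mITT population, and likewise in the per-protocol population, with death, uTVR or REPLACE-2 major bleeding in the window as a composite event regardless of troponin.
2. Treat the composite as missing only for patients with none of these events whose PPM status cannot be evaluated under the troponin rule, with one stated rule for all missing-baseline patients. Keeping those below 3 × ULN as non-events while dropping those at or above it would bias the rate down: 0.51(1 − m)/[(1 − m) + 0.49m] gives 49.7% or 48.4% at m = 5% or 10% missing baseline, if 51% of them reach 3 × ULN.
3. List death, uTVR and major bleeding for both missing-troponin groups, and replace the intention-to-treat reference with mITT.

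In SAP 3.13:

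4. Report the remaining missing patients by arm. Add a sensitivity analysis setting them all to non-event, all to event, and worst case for the test arm (test = event, control = non-event), for all three comparisons with actual arm sizes.

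The downside is that items 1 and 2 together keep troponin-missing patients only when they have an event, which raises the observed rate somewhat. With m the missing fraction and q the non-PPM event rate among them, the rate becomes [0.51(1 − m) + mq]/[(1 − m) + mq]. At m = 10% this is 51.5%, 52.3% or 53.6% for q = 10%, 25% or 50%. Both m and q are assumptions; item 4 shows the effect.

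The cost is a few sentences, one derivation change and one sensitivity table, with no new data.
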